5. STUDY DESIGN, PROCEDURES AND METHODOLOGY

5.1 Study design

The research will adhere to a randomized, double-blind, 2-arm parallel-groups design. Participants will engage remotely from their home. The entire study duration is set at 3 days.

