The first HRV measurement will serve as testing purposes and will be taken immediately after the survey that will prompt participants to go to a quiet place just after the start of the experiment. The additional HRV measurements will be taken twice daily, immediately following the completion of each Ecological Momentary Assessment (EMA).

One-time measurement (end of the trial)

Usability of the intervention to assess the usability of the current pilot trial, a set of questions will be asked to assess the participants' experiences with the mindfulness and sham meditation tracks in terms of ease of use, clarity of instructions, relevance to daily life, engagement levels, comfort, perceived efficacy, willingness to continue usage, any technical issues encountered, and suggestions for improvement.

Perceived Awareness of the Research Hypothesis (PARH; Rubin 2016) is a four-item quantitative self-report tool designed to assess the possible impact of demand characteristics in research settings. Its purpose is to assist in challenging the notion that observed effects can be attributed to demand characteristics. Participants provide their responses to these statements using a 7-point Likert-type scale, where the options range from strongly disagree (1) to strongly agree (7). Examples of statements include: "I was aware of the researchers' objectives in this study" and "I was uncertain about the researchers' intentions in conducting this research".

Expectancy and credibility of the intervention

To assess expectancy, we will use a single item adapted from the Credibility/Expectancy Questionnaire (Devilly & Borkovec, 2000) during the final phase of post-intervention testing: "On a scale from 0 to 10, How effective do you believe the meditation training has been in alleviating stress? (0 = Not at all successful, 10 = Extremely successful)."

To evaluate credibility, participants will respond to a two-part question: "If you were informed that you might have received either meditation training or control training, which type do you believe you received? (Meditation, Control)". "How confident are you in your answer? (0 = Not at all confident, 10 = Extremely confident)".

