Participants will then be randomly assigned by the Qualtrics engine to either the experimental group, which listens to a mindfulness audio track, or the control group, which listens to a 'sham meditation' track. Both tracks are embedded within the Qualtrics survey. Participants cannot skip this portion of the survey for 10 minutes, ensuring they listen to the entire 10-minute audio track. Afterward, participants will be asked to sit quietly for three minutes without engaging in any activities. This pause is necessary because, some of the audio track encompasses the application of mindfulness principles while performing a routine activity (e.g., brushing teeth) during the listening of a mindfulness track. Although the movement involved in this activity is minimal, we want participants to sit still for three minutes to avoid introducing any confounding variables in the subsequent HRV assessments. The survey will be programmed to remain stuck during this period to prevent participants from skipping this step.

Following the quiet period, participants will complete post-intervention assessments for STAI-6, EMA and HRV. Participants will be thanked and instructed to reopen the survey link the following day, ideally at the same time between 9am and 9pm. On Day 2, they will complete the same pre-intervention assessments (STAI-6, EMA and HRV), listen to a different audio track, either mindfulness or sham meditation, depending on their group allocation, sit for three minutes, and then complete the post-intervention assessments mirroring Day 1. On Day 3, participants will undergo the same procedure as Day 2 but will listen to another audio track (mindfulness or sham). Additionally, they will complete the FFMQ, answer questions about their expectations of the intervention, its credibility, the PARH scale, and the usability questionnaire. Finally, participants will be thanked for their participation in the study and debriefed.

6. Ethics information

This study will be conducted in accordance with the ethical principles outlined in the Declaration of Helsinki and in compliance with applicable regulatory requirements. The final study protocol, along with the latest version of the Participant Information and Consent Form, will receive written approval from the A*STAR Institutional Review Board (A*STAR IRB) before any participants are enrolled.

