8. SAMPLE SIZE AND STATISTICAL METHODS

8.1. Determination of Sample Size.

Since this is a pilot trial, we aim to recruit 60 participants to account for a ~20% dropout rate, ensuring we meet our target of at least 50 participants.

8.2. Statistical analyses.

Our confirmatory statistical analyses will include:

- Bayesian mixed-effects models to investigate the longitudinal changes in self-reported stress measured via STAI-6. The model will have STAI-6 as the

dependent variable, with 'Group' (mindfulness intervention or control), 'Day' (1 to 3), and their interaction term as independent variables. Participant ID will be used as a random intercept to control for individual differences. A BF10 greater than 1 will indicate slightly positive evidence supporting the effectiveness of the mindfulness condition over the control condition in stress reduction.

We will also conduct the following exploratory statistical analyses:

- A Bayesian mixed-effects model to assess longitudinal changes in HRV, using HRV as the dependent variable and 'Group', 'Day' (1 to 3), and their interaction as independent variables. Participant ID will again serve as a random intercept. A BF10 greater than 1 will suggest positive evidence for the mindfulness intervention's effectiveness compared to the control.
- An additional Bayesian mixed-effects model will analyze longitudinal changes in HRV, with the dependent variable being HRV (calculated by the difference in pre- and post-meditation HRV scores) and independent variables including 'Group', 'Day' (1 to 3), and their interaction. Participant ID will account for individual variability in baseline HRV levels.
- Correlational analyses to explore the relationship between changes in mindfulness scores and stress levels, as well as between HRV changes and stress levels.
- Descriptive statistics to summarize baseline participant characteristics, such as neuroticism, RS-14 scores, FFMQ scores related to mindfulness training, and demographic details.
- Analysis of responses regarding the intervention's credibility and participant awareness of the research hypothesis to assess equal credibility of the intervention for the mindfulness condition and the sham.

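### The second exploratory HRV model says Participant ID accounts for baseline HRV, but on a difference score it cannot; the cost is modest precision and exposure to chance Day 1 imbalance, not bias

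*Combined protocol and SAP*

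**What the plan says.** Section 8.2 lists two exploratory Bayesian mixed models for HRV. The first takes HRV itself as outcome, and there "Participant ID will again serve as a random intercept". The second takes a difference as outcome, "calculated by the difference in pre- and post-meditation HRV scores", with "independent variables including 'Group', 'Day' (1 to 3), and their interaction". It then states: "Participant ID will account for individual variability in baseline HRV levels". The second bullet does not repeat that the participant term is a random intercept; I read it so from the bullet before. Neither model names a baseline HRV covariate, and nothing elsewhere in the document qualifies the sentence.

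On timing, section 5.3.2 describes a test reading at the start, and then: "The additional HRV measurements will be taken twice daily, immediately following the completion of each Ecological Momentary Assessment (EMA"). That gives one pre-session and one post-session value on each of three days. Section 5.4 places allocation after the Day 1 pre-session reading: "Participants will then be randomly assigned by the Qualtrics engine to either the experimental group". Day 1 pre-session HRV is therefore a true baseline. The Day 2 and Day 3 pre-session values are not.

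**The concern.** The sentence fits the first HRV model, where the outcome is HRV and a participant intercept does represent that person's level. Attached to the second model, it gives the intercept a job that the subtraction has already done, and implies a baseline adjustment that no term provides. Change remains negatively related to the Day 1 pre-session value through regression to the mean, and the model does not use that relation.

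Two things are at stake. An arm difference in Day 1 pre-session HRV that arises by chance carries partly into the Day 1 contrast on change. The contrast is also less precise than it could be with a value the trial already collects. In addition, the pilot is meant to lay the ground for a larger multi-site trial, so an incorrect description of the model may be copied forward.

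**Working it through.** The plan states no HRV standard deviation, correlation or effect size, so there is no figure of its own to reproduce.

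**Inputs.** Section 5.1 gives a "randomized, double-blind, 2-arm parallel-groups design"; 1:1 allocation is my assumption. Section 8.1 says "we aim to recruit 60 participants to account for a ~20% dropout rate, ensuring we meet our target of at least 50 participants", so I take 25 per arm. The within-session pre/post correlation ρ is not given; I assume 0.5 to 0.8 and show values outside that range. Pre and post variances are taken as equal (s²), and the difference as post minus pre.

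**1. What the intercept can capture.** Write HRV as participant level + day level + residual. Pre and post values on one day share the first two parts, so post minus pre = residual(post) − residual(pre) + session effect. The participant level is gone. In simulated data (50 participants, 150 data sets per scenario, ρ of 0.5, 0.7 and 0.9, no true variation in response), the participant-level variance of HRV was 0.4 to 0.8. The median intercept variance estimated from the differences was 0.001 to 0.003.

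**2. What is left unused.** Corr(pre, change) = −√((1−ρ)/2), which is −0.50 at ρ = 0.5 and −0.32 at ρ = 0.8.

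**3. Day 1 variance.** Change score: 2s²(1−ρ). Adjusted for Day 1 pre-session HRV: s²(1−ρ²). Ratio = (1+ρ)/2.

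**4. Three-day average.** In this model, changes on different days are uncorrelated, and Day 1 pre-session HRV is unrelated to change on Days 2 and 3. Only one of three equal parts shrinks, so the ratio = [(1+ρ)/2 + 2]/3 = (5+ρ)/6.

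| ρ | Day 1 ratio | Three-day ratio |
|---|---|---|
| 0.3 | 0.65 | 0.88 |
| 0.5 | 0.75 | 0.92 |
| 0.8 | 0.90 | 0.97 |
| 0.9 | 0.95 | 0.98 |

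Estimating the slope with 50 participants multiplies each adjusted variance by about 1 + 1/46 = 1.022. At ρ = 0.5 to 0.8 the Day 1 ratio becomes 0.77 to 0.92 and the three-day ratio 0.94 to 0.99. Simulation agrees (Day 1 about 0.77 to 0.93, three-day about 0.94 to 0.99). If participants also differ in true response, the three-day ratio can reach 1.00.

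**5. Chance imbalance.** One standard error of the arm difference in Day 1 pre-session HRV is √(2/25) = 0.28 SD. It shifts the Day 1 change contrast by (1−ρ) × 0.28, that is 0.14 SD at ρ = 0.5 and 0.06 SD at ρ = 0.8. The three-day average shifts by a third of that: about 0.05 and 0.02 SD.

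**6. Same-day pre-session HRV as covariate.** Suppose the intervention shifts the Day 2 and Day 3 pre-session values by δ. The difference score removes δ in full. A covariate with slope β below 1 leaves (1−β)δ in the group effect. Take a true within-session effect of 0.30 SD, an assumed δ of 0.30 SD on two of the three days, and β of about 0.36. The expected three-day estimate is 0.30 + (2/3)(1 − 0.36)(0.30) = 0.43. A small simulation (60 runs, 25 per arm, ρ = 0.5) gave 0.44, against about 0.30 for the difference score.

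**The case against.** The best defence is that a difference score with Group, Day and their interaction is a legitimate analysis of within-session change. It adjusts for each session's starting value with a slope of 1, it removes stable differences between participants entirely, and randomisation makes the contrast unbiased. Only one of the three pre-session values is a randomised baseline, so the usual advantage of covariate adjustment applies to one day in three. The model is exploratory, second of two for HRV, and its bullet carries no Bayes factor threshold; the confirmatory model uses STAI-6. The word introducing the predictors also leaves the covariate list open.

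All of that stands, and it limits the size of the point. It does not rescue the sentence, because no covariate is named and the intercept cannot supply the stated adjustment. Exact cancellation does assume an additive participant level. If change scales with level, the intercept may absorb some level-related variation in change, but it still would not adjust the arm contrast for baseline.

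A reader might infer that baseline is not handled at all, or that the HRV effect is systematically biased. Neither follows, for the reasons just given. A reader might also infer that the difference should be replaced by post-session HRV adjusted for same-day pre-session HRV, with the same estimand. The timing in section 5.4 speaks against this: on Days 2 and 3 that covariate is measured after randomisation, and with carry-over between days the within-session effect is distorted, as step 6 shows.

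**Conclusion.** The statement about Participant ID is wrong for the difference-score model and should be corrected. The statistical consequence is small: a useful precision gain is forgone on Day 1, little or none over the three-day average, with a matching mild exposure to chance imbalance in Day 1 pre-session HRV. The sizes rest on the assumed ρ of 0.5 to 0.8, equal pre and post variances, an additive participant level and 25 per arm. At ρ = 0.9 or above the gain almost vanishes; at 0.3 it would be larger. The cancellation itself does not depend on ρ. Priority is low.

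**What to change.** In section 8.2, keep the difference score as outcome and specify: change in HRV ~ Group × Day + Day 1 pre-session HRV × Day + (1 | Participant). The covariate is the pre-intervention reading taken before randomisation, not the test reading. Its slope may differ by Day, because its relation to change is expected mainly on Day 1. Do not substitute the same-day pre-session value on Days 2 and 3.

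Replace the sentence on Participant ID with one saying that the participant intercept models the correlation among a participant's repeated change scores, and that baseline HRV enters through the covariate.

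The cost is one or two lines, no new data and three extra parameters (one slope and two slope-by-Day terms). Section 5.3.2 lets participants move on after a third failed reading, so the text should also say how a missing Day 1 pre-session value is handled; otherwise those participants would drop out of the adjusted model.

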5.3.1 One-time measurement (start of the trial)

The following psychological and self-reported assessments will be taken at baseline. Participants will be starting the survey at home in a quiet place.

Neuroticism subscale of the IPIP (IPIP-20; Goldberg et al., 2006) - 5 NEO

domains. The scale consists of 20 items to assess the self-reported levels of neuroticism. Examples of items are "I often feel blue" or "I am filled with doubts about things" (answered on a five-point scale ranging from 1 = Very inaccurate to 5 = Very accurate).

Resilience Scale 14 (RS-14; Mirošević et al., 2019)

The RS-14 is a brief version of the Resilience Scale, comprising 14 items. Each item is rated on a 7-point Likert scale, ranging from 1 to 7. Examples of items are "I usually manage one way or another" or "I am determined". Higher resilience scores are associated with improved mental health, enhanced quality of life, and reduced levels of anxiety and depression.

Demographics Participants will provide demographic information, including age, gender, ethnicity, type of smartphone used for the experiment, as well as its operating system (iOS or Android) and version.

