The Qualtrics link contains the written informed consent form and the actual experiment. Participants will be able to review all relevant information about the study and either accept or decline to participate. If they do not provide consent, they will be opted out of the study. If consent is provided, participants will proceed to the second screening, which involves answering additional questions about their use of concomitant medication. If they meet the criteria for this stage, they will proceed to answer questions about any neurological or psychiatric conditions. If any of the screening criteria are not satisfied at any point, the study will automatically terminate. Once consent and second screening are complete, participants will then be instructed to move to a quiet environment where they will not be disturbed for the next 35 minutes. They will be asked to download the 'Camera Heart Rate Variability' app and take an initial HRV measurement for testing purposes. Participants will then submit the generated CSV file to the study coordinator via WhatsApp and self-report their rMSSD values in the Qualtrics survey. Participants are instructed to label their CSV files using their anonymous identifier provided by the study coordinator via WhatsApp at the start. Afterward, they will complete a series of questionnaires, including the 20-item IPIP scale, the RS-14, the FFMQ, and various demographic questions such as age, gender, ethnicity, smartphone type used during the experiment, and its operating system (iOS or Android) and version. Pre-intervention assessments of STAI-6, EMA will also be conducted. They will then use the 'Camera Heart Rate Variability' app to measure HRV, submit the generated CSV file to the study coordinator, and self-report their rMSSD values in the Qualtrics survey, as outlined in the instructions.

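### The confirmatory STAI-6 model has no baseline covariate, although Day 1 pre-track STAI-6 and neuroticism are measured before randomisation, so the Group contrast is less precise than the collected data allow

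*Combined protocol and SAP*

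**What the plan says.** All references are to the combined protocol and SAP.

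- **Confirmatory model (8.2).** STAI-6 is the "dependent variable, with 'Group' (mindfulness intervention or control), 'Day' (1 to 3), and their interaction term as independent variables". For the random part, "Participant ID will be used as a random intercept to control for individual differences". No baseline covariate is named.
- **Decision rule (8.2).** "A BF10 greater than 1 will indicate slightly positive evidence supporting the effectiveness of the mindfulness condition over the control condition in stress reduction". The model term behind this Bayes factor is not identified.
- **Trait scales (5.3.1 and 5.4).** Of the neuroticism measure: "The scale consists of 20 items to assess the self-reported levels of neuroticism". On Day 1, "Afterward, they will complete a series of questionnaires, including the 20-item IPIP scale, the RS-14, the FFMQ, and various demographic questions". The pre-track STAI-6 follows, and only then does the Qualtrics engine allocate participants. No stratification is mentioned.
- **Use of the trait scales (8.2).** Neuroticism and RS-14 appear only under "Descriptive statistics to summarize baseline participant characteristics, such as neuroticism, RS-14 scores". The mindfulness questionnaire has a further role: "Correlational analyses to explore the relationship between changes in mindfulness scores and stress levels".
- **STAI-6 schedule (5.3.2, repeated measurements).** It is taken before and after each track on three days, giving six readings per person. Section 8.2 does not say which of the six are outcomes.

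**The concern.** The plan gives the random intercept the job of controlling for individual differences. It does so only in part. It tells the model that readings from one person are correlated, so that the standard errors are honest. It does not take stable differences between people out of a comparison between two groups of different people. Only a covariate measured before allocation can do that.

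With about 25 people per arm, those stable differences make up most of the variance of the Group contrast. The most direct measure of them, the Day 1 pre-track STAI-6, is already collected, and so is neuroticism. If the Bayes factor tests the Group effect, it would be computed from a less precise estimate than the data permit, in a study that section 2 expects to show only a modest effect. Since the analysis is labelled confirmatory and will be registered, a covariate added after the data are seen would be post hoc.

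**Working it through.** **The plan's own figure.** Section 8.1 states: "we aim to recruit 60 participants to account for a ~20% dropout rate, ensuring we meet our target of at least 50 participants". 50 × 1.2 = 60 reproduces the recruitment target. (Dividing by 0.8 would give 62.5, so 63, and a 20% loss from 60 leaves 48; this does not affect the point.) No SD, effect size, power or precision is stated, so nothing further can be reproduced. I use N = 50 completers.

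**Assumptions not in the documents**
- 1:1 allocation, so 25 per arm.
- Outcome: the mean of the three post-track readings, in units of the SD of a single reading.
- Equal correlation (ICC) between any two STAI-6 readings of one person, including the Day 1 pre-track reading: 0.6, range 0.4 to 0.8.
- Correlation r between neuroticism and a single STAI-6 reading: 0.2 to 0.5.
- Estimating k covariates multiplies the variance by 1 + k/(N − 2 − k − 1).

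**Step 1: model as written.** The variance of a person's mean is ICC + (1 − ICC)/3 = 0.6 + 0.4/3 = 0.733. SE(Group) = √(0.733 × 2/25) = 0.242.

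**Step 2: add Day 1 pre-track STAI-6.** It explains ICC² = 0.36, leaving 0.373. With k = 1 the factor is 1 + 1/46 = 1.0217, giving 0.381. SE = √(0.381 × 2/25) = 0.175, a reduction of 27.9%. The equivalent unadjusted sample is 50 × 0.733/0.381 ≈ 96.

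**Step 3: add neuroticism as well.** The two covariates together explain (ICC² − 2·ICC·r² + r²)/(1 − r²). At ICC 0.6 this is (0.36 − 0.2r²)/(1 − r²). With k = 2 the factor is 1 + 2/45 = 1.0444.
- r = 0.2: explained 0.367; remaining 0.367 × 1.0444 = 0.383. Against 0.381 in step 2, the SE rises by 0.2%.
- r = 0.5: explained 0.413; remaining 0.320 × 1.0444 = 0.334. The SE falls by a further 6.4%.

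**Step 4: range over the assumed ICC**

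| ICC | SE, no covariate | SE, Day 1 STAI-6 | Reduction | Further reduction from neuroticism, r = 0.2 / 0.3 / 0.4 / 0.5 |
|---|---|---|---|---|
| 0.4 | 0.219 | 0.190 | 13.4% | 0.6% / 3.1% / 7.1% / 13.8% |
| 0.6 | 0.242 | 0.175 | 27.9% | −0.2% / 1.1% / 3.1% / 6.4% |
| 0.8 | 0.263 | 0.136 | 48.3% | −0.7% / −0.2% / 0.6% / 1.9% |

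A negative figure is a loss of precision. At ICC 0.6, neuroticism alone would lower the SE by 1.7% (r = 0.2) to 17.9% (r = 0.5).

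**Step 5: Group by Day.** A covariate that is constant over days cancels out of each person's slope. With days coded −1, 0, 1 the slope variance is 0.4/2 = 0.2, and SE = √(0.2 × 2/25) = 0.126, with or without covariates.

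**Step 6: simulation check.** In 4000 simulated trials at ICC 0.6 and r = 0.4, the Group SE was 0.242 with no covariate, 0.215 with neuroticism, 0.174 with Day 1 STAI-6 and 0.168 with both. The Group by Day SE was 0.127 in all four models.

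**Step 7: cost.** One uninformative covariate raises the SE by √1.0217 − 1 = 1.1%; two raise it by √1.0444 − 1 = 2.2%.

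**The case against.** **The test may be of the interaction.** Section 8.2 speaks of longitudinal change and includes Group by Day. If BF10 tests that term, the gain is zero. This stands. A reader might infer that the confirmatory test as a whole loses precision; the documents support this only for the Group contrast and do not say which term is tested.

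**Adjustment is not free.** A reader might infer that using the trait scores costs nothing. That is true of data collection only. Each covariate uses a degree of freedom, and a weak one added after Day 1 STAI-6 can lose precision, as the r = 0.2 result at ICC 0.6 shows.

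**Neuroticism is not the main omission.** A reader might take the unused trait scores to be the chief loss. Under the assumed ICCs of 0.6 and 0.8, Day 1 STAI-6 does more than neuroticism for any r up to 0.5. Only at the low ICC of 0.4 with r above 0.4 would neuroticism do more. Nor are all the trait scales purely descriptive: changes in mindfulness scores enter the exploratory correlations.

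**Chance imbalance is not bias.** A reader might infer that without adjustment the Group estimate is biased. Under randomisation it is not; its standard error already allows for chance imbalance. The loss is one of precision.

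**It is a pilot with no precision target.** True, and leaving out an optional covariate contradicts nothing in the plan. This limits the severity. It does not remove the case for a cheap change to an analysis the plan itself calls confirmatory.

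**Conclusion.** The point holds as a modest improvement to 8.2. The confirmatory model omits baseline information collected before allocation, and the random intercept does not take its place in the Group contrast. On assumed values (ICC 0.6, 25 per arm, equal correlation among readings), Day 1 pre-track STAI-6 lowers the Group SE by about 28%, with a range of 13% to 48% for ICC 0.4 to 0.8. Neuroticism then adds between a 0.2% increase and a 6% reduction at ICC 0.6. These sizes rest on correlations that the documents do not give; the direction for Day 1 STAI-6 is the same across the range examined. The benefit is confined to the Group effect and depends on the plan naming that as the tested term.

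**What to change.** In 8.2:

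1. Define the outcome as the post-track STAI-6 readings on Days 1 to 3, all taken after randomisation.
2. Add Day 1 pre-track STAI-6 as a fixed-effect covariate and exclude that reading from the outcome rows. Otherwise the same measurement would stand on both sides of the model.
3. State that BF10 tests the Group effect adjusted for baseline. Because the interaction stays in the model, centre Day so that the Group coefficient is the average over days.
4. Report the unadjusted model as a sensitivity analysis. Comparing the two also gives an estimate of the variance reduction for planning the later multi-site trial.
5. Optionally, pre-specify neuroticism as one further covariate. Do not add the trait scales as a set: six uninformative covariates would raise the SE by about 7%, since √(1 + 6/41) = 1.071.

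The cost is a few sentences and no new data, plus one or two degrees of freedom: about 1.1% of the SE for each covariate that proves uninformative with 50 completers.
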